From [name] data we use $\text{mean}[R(0, j)] = 2.54$; $\text{sigma}[R(0, j)] = 4.04$. We expect a decrease in R in both groups, on average about one standard deviation. Then the difference post-pre = 4.04 in each group, save for statistical variability. For equivalence interval for comparison of treatments 1 and 2, we take 3/4 of the standard deviation, namely 3.03. For 20% expected drop-out, we have $n_1 = n_2 = 32$, power analysis is provided below. We use PASS (www.NCSS.com) for computation. The procedure presented below can be described as follows (PASS Manual, Chapter 260). "This procedure allows you to study the power and sample size of equivalence tests of the means of two independent groups using the two-sample t-test. Schuirmann's (1987) two one-sided tests (TOST) approach is used to test equivalence. For a comprehensive discussion, refer to Chow and Liu (1999)." Essentially, two one sided tests with alpha and beta provide an equivalence test.

Power Analysis of Two-Sample T-Test for Testing Equivalence Using Differences Numeric Results for Testing Equivalence Using a Parallel-Group Design

Reference Treatment	Group Sample	Group Sample	Lower	Upper

Power	Size (N1)	Size (N2)	Equiv. Limit	Equiv. Limit	True Difference	Standard Deviation	Alpha	Beta
0.52	32	32	-2.02	2.02	0.00	4.04	0.10	0.48
0.81	32	32	-3.03	3.03	0.00	4.04	0.05	0.19
0.91	32	32	-3.03	3.03	0.00	4.04	0.10	0.09

The normality assumption for the ratio R will be checked, and data will be logarithmically transformed if the normality assumption does not hold. Assuming log-normal distribution, mean of 2.54 and SD=4.04 on the original scale correspond to mean $m=0.3015$ and $SD_{\log} = 1.12$ on the log-transformed scale. Further assuming equal variances across time points in both treatment arms, and within-subject correlation 0.5 between pre- and post-treatment values (as above), the standard deviation of changes will also be $SD_{D,\log} = 1.12$. The equivalence margin on the log-scale will then be $\delta = 3/4*SD_{D,\log} = 0.8423$.

Based on the TOST procedure, equivalence will be established at $\alpha=0.05$ significance level if the $(1-2\alpha)\times100\%$ CI for the difference is contained within the interval $(-\delta, \delta)$. The overall p-value for the equivalence test will be the larger of the p-values of the two one-sided tests.

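### Section 13.4 lets an unspecified normality check choose between two different equivalence hypotheses, and the raw-scale limits (±3.03) are wider than the whole baseline mean (2.54)

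*Combined protocol and SAP*

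**What the plan says.** The primary outcome is R, the Ki-67 index divided by the BAX index. Section 13.4 takes each participant's raw change, D = R at 12 weeks minus R at baseline, and compares mean D between the two aspirin arms. The limits rest on earlier trial data with mean 2.54 and SD 4.04: "For equivalence interval for comparison of treatments 1 and 2, we take 3/4 of the standard deviation, namely 3.03". The power table, with 32 per arm, is on this raw scale and gives 0.81 at α = 0.05.

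After the table the section adds: "The normality assumption for the ratio R will be checked, and data will be logarithmically transformed if the normality assumption does not hold". It converts the planning values to a log mean of 0.3015 and a log SD of 1.12. It keeps 1.12 as the SD of the log change (pre-post correlation 0.5) and sets a second margin: "The equivalence margin on the log-scale will then be" 0.8423, again three quarters of an SD.

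The variable to be checked is named (R). The test, the threshold, the visit, whether arms are pooled, and whether the check is made blind to arm are not. The primary test involves only the two aspirin arms. Section 13.5 uses placebo as a background reference in the secondary analyses.

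**The concern.** In an equivalence trial the claim is the margin on its scale. Here the trial's own data, through a check with no stated rule, decide which of two claims is tested: that mean raw changes differ by less than 3.03, or that the ratio of geometric means lies between 0.43 and 2.32. These are not two versions of one hypothesis.

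The raw version has a further problem. R is a ratio of two non-negative fractions (section 8.2), so mean R can fall by at most its baseline value, 2.54. The raw limits are wider than that. An intermittent schedule that does nothing would therefore meet the raw definition of equivalence, and the primary test has no comparison with placebo to expose it.

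**Working it through.** **Inputs (section 13.4):** baseline mean 2.54; SD 4.04; correlation 0.5, so the SD of change is also 4.04 raw and 1.12 log; n = 32 per arm; α = 0.05 for each one-sided test; margins 3.03 and 0.8423.

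**1. The plan's own figures.**
- SE = 4.04 × √(2/32) = 1.01. With a true difference of 0, approximate power is 2Φ(3.03/1.01 − 1.645) − 1 = 2Φ(1.355) − 1 = 0.825. The exact t calculation gives 0.814, against 0.81 stated. The other two rows give 0.519 and 0.911, against 0.52 and 0.91.
- Log SD = √ln(1 + (4.04/2.54)²) = 1.123; log mean = ln 2.54 − 1.123²/2 = 0.3015; margin = 0.75 × 1.123 = 0.8423. All agree. Exact log-scale power is also 0.814.

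**2. What each margin allows.**
- Log: exp(±0.8423) = 0.431 and 2.322. An inert arm lies outside these limits once daily aspirin lowers R by more than 1 − 0.431 = 57%.
- Raw: 3.03/2.54 = 119% of the baseline mean. If daily aspirin drove R to zero and the intermittent schedule changed nothing, the difference would be 2.54, still inside ±3.03.

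**3. How often an inert arm would be declared equivalent.** Lying inside the limits does not guarantee a pass. The 90% CI half-width at SD 4.04 is about 1.69, so the observed difference must be within 3.03 − 1.69 = 1.34. The plan gives no attainable effect for daily aspirin, so the fall in mean R is an assumption and is varied. The log-normal column comes from 20,000 simulated trials per setting; its range covers reading the 0.5 correlation on the log or the raw scale.

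| Fall in mean R on daily aspirin | Raw ±3.03, normal | Raw ±3.03, log-normal R | Log ±0.8423 |
|---|---|---|---|
| 30% | 0.70 | 0.71–0.78 | 0.52 |
| 50% | 0.53 | 0.62–0.68 | 0.13 |
| 60% | 0.43 | 0.54–0.60 | 0.03 |
| 70% | 0.34 | 0.46–0.52 | under 0.01 |
| 80% | 0.25 | 0.37–0.41 | 0.00 |

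**4. Which branch the check would select.** A normal R with mean 2.54 and SD 4.04 would be negative in Φ(−2.54/4.04) = 26% of cases, which is impossible for this ratio. In log-normal simulation (2,000 trials per setting), Shapiro-Wilk at 0.05 (assumed, since the plan names no test) accepted baseline R, 64 values, in 0% of trials. It accepted the raw changes in both arms in under 1%.

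**5. If R were less variable.** Assume SD 1.27 with mean 2.54. The fixed raw margin is then 3.03/1.27 = 2.4 SD. On the raw scale an inert arm passes in at least about 92% of trials for falls of 30% to 80%. On the log scale it passes in 35% at a 50% fall and 0% at 70–80%.

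**The case against.** The strongest reply is that, on the plan's own figures, the raw branch would hardly ever be entered. That stands. A reader might infer from step 3 that the trial as planned has a high chance of calling an inert schedule equivalent. The documents do not support this: with a formal check at the planned variability, the two-stage procedure behaves like the log test alone, and there is no inflation.

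A reader might also infer that the raw test would usually pass an inert schedule. That too is unsupported without a condition on the effect of daily aspirin. The plan's only figure for that effect is "We expect a decrease in R in both groups, on average about one standard deviation. Then the difference post-pre = 4.04 in each group". A fall of 4.04 exceeds the mean of 2.54 and cannot occur in a non-negative ratio; taken literally it would let an inert arm pass only 0.4% of the time.

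Three further points are fair. Both margins are numbers fixed in advance by one rule; the data settle only which of them applies. Passing an inert arm on the raw scale is not a type I error for the raw hypothesis, because the true difference lies inside its limits; the fault is in the hypothesis. And the planning values may themselves be misread. In the table in 13.4 the surface and bottom ratios are reciprocals of each other with identical SDs, which suggests geometric summaries (an inference; the overall rows do not match this way). If 4.04 were a geometric SD, the log SD would be ln 4.04 = 1.40 and log-scale power at 0.8423 about 0.54. The comparisons with 2.54 as an arithmetic mean would also need redoing.

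None of this justifies keeping the branch. If it is never used it serves no purpose, yet the definition of D and the power table still rest on it. If it is used, either the check was informal or R proved less variable than assumed, and in the second case ±3.03 is at its loosest. Section 13.4 itself concedes that little is known about R.

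**Conclusion.** The point holds in a limited form. Section 13.4 does not fix the primary scale or hypothesis, and one of its two branches has limits that cannot exclude an inert intermittent schedule. That second statement needs only a non-negative R and an arithmetic baseline mean of 2.54.

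The size of the effect is conditional. With the raw test at SD 4.04 and 32 per arm, an inert schedule passes more often than not if daily aspirin lowers mean R by up to about half (normal) or about 60% to 70% (log-normal), and less often beyond that. At a 50% fall the raw figure is 53% to 68%, about 60%, against about 13% on the log scale. The practical exposure is an informal check or unexpectedly low variability.

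Fixing the scale does not settle whether the log margin is tight enough: at a 30% fall an inert arm still passes it 52% of the time. That margin needs its own justification.

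**What to change.** In section 13.4:
- Name log(R) as the only primary scale, and redefine D as the change in log(R) from baseline to 12 weeks.
- Apply the two one-sided tests to the difference in mean D with the pre-stated margin 0.8423, expressed also as a ratio of geometric means of 0.43 to 2.32.
- Delete the conditional transformation, restate the power calculation on the log scale, and report raw-scale results descriptively.

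This is a free improvement: SAP wording only, with no change to participants, visits or assays. Both margins are 0.75 SD, so planned power stays about 0.81 with 32 per arm if the plan's log SD of 1.12 is right. Whether 2.54 and 4.04 are arithmetic or geometric summaries should be confirmed at the source at the same time.

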13.5 Secondary and Exploratory Objectives, Endpoints, Analysis Plans

The secondary objectives are to evaluate the effects of aspirin treatments on:

- 1) the ratio of cell proliferation (Ki-67)/apoptosis (TUNEL) in rectal biopsies
- 2) the ratio of cell proliferation (Ki-67)/necroptosis (pMLKL) in rectal biopsies
- 3) fecal occult blood test (measures of adverse events) as measured by stool samples

The exploratory objectives are to evaluate the effects of aspirin treatments on:

- 1) COX-2 in rectal biopsies
- 2) BAX in rectal biopsies
- 3) TRPM7 in rectal biopsies
- 4) joint index of COX-2 with TRPM7 expression in rectal biopsies;
- 5) joint index of TRPM7 with BAX in rectal biopsies;
- 6) methylation assays using the MethylationEPIC BeadChip to identify methylation biomarkers in genes (i.e. CDKN2A (cell cycle regulation), MGMT (DNA repair), DAPK1(apoptosis), CDH1(cell invasion), WNT16 (Wnt pathway) and RASSF1 (RAS signaling)) involved in colorectal carcinogenesis, and other epigenome-wide methylation biomarkers as measured in rectal biopsies;
- 7) metagenomics analysis to measure abundance of *E. coli* and *Fusobacterium* and other microbiota in rectal swabs

The majority of secondary and exploratory endpoints are continuous. Biomarker levels at baseline, 9 and 12 weeks, as well as the corresponding changes from baseline, will be summarized using descriptive statistics including means and standard deviations or medians and interquartile range, as well as graphical methods such as “spaghetti plots” that depict change patterns over time. Distributions of each marker will be examined, and values may be transformed as needed to stabilize the variance or satisfy the normality assumption. Correlation between biomarkers, and between pre- and post-treatment values will be examined using scatterplots with overlayed smoother plots for ease of visual interpretation.

If the normality assumptions are satisfied, paired t-tests will be used to examine whether the biomarkers change from baseline to 12 weeks post-treatment in each treatment arm. Signed rank test will be used if no suitable transformation can be found. Because we expect that the continuous and intermittent dosing regimens will result in similar biomarker changes, we will use the TOST procedure, similar to the primary

endpoint, to test for equivalence. The equivalence margin will be set as 3/4 of the observed standard deviation of the marker at baseline, similar to the primary endpoint.

Additional analyses will be conducted using linear mixed effects models with repeated measures to further explore biomarker change patterns over time across 3 time points, and to compare them between arms. These models use all available observations accommodating data that are missing at random, rather than performing a complete case analysis.

A placebo arm is included in the secondary analyses because the variations on repeated measurement of the new biomarkers of methylation and microbiota are not known from the previous trials, and therefore changes in the treatment arms are difficult to interpret. The placebo arm is used as a reference for background, as a cohort for analysis.

Fecal occult blood tests will be categorized as binary (present vs. absent) at each time visit. Proportion of patients with at least one positive test will be compared between arms using Fishers exact test because incidence of this adverse event is expected to be low.

Exploratory endpoints of joint index of COX-2 with TRPM7 and joint index of TRPM7 with BAX in rectal biopsies will be analyzed similarly. Indices will be calculated using a scoring approach based on factor analysis.

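### For the continuous secondary and exploratory markers, Section 13.5 tests change within each aspirin arm and equivalence between regimens, but names no aspirin-versus-placebo contrast as the basis for stating an aspirin effect

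*Combined protocol and SAP*

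**What the plan says.** Section 13.5 introduces the secondary endpoints with "The secondary objectives are to evaluate the effects of aspirin treatments on" the listed markers, and uses the same aim for the exploratory ones.

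For continuous markers it names two tests:
- Within arm: "paired t-tests will be used to examine whether the biomarkers change from baseline to 12 weeks post-treatment in each treatment arm", with a signed rank test if no transformation gives normality.
- Between the two aspirin regimens: "we will use the TOST procedure, similar to the primary" endpoint, with a margin of three quarters of the marker's observed baseline SD.

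It then lists additional linear mixed models, whose purpose is "to further explore biomarker change patterns over time across 3 time points, and to compare them between arms".

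The sentence on placebo begins: "A placebo arm is included in the secondary analyses because the variations on repeated measurement of the new biomarkers of methylation and microbiota". Its point is that earlier trials have not established this variability, and it concludes: "therefore changes in the treatment arms are difficult to interpret". The role given is: "The placebo arm is used as a reference for background, as a cohort for analysis".

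Fecal occult blood is handled differently: "Proportion of patients with at least one positive test will be compared between arms using Fishers exact test".

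The schedule in Section 7.1 and the collection procedure in Section 10.2.1 put rectal biopsies at Clinic Visits 2, 3 and 4 with no exception for the placebo arm.

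**The concern.** The objective is causal, but the named significance test of change is not comparative. A paired test from baseline to week 12 asks whether a marker moved. Any movement shared by all participants (time on study, repeat biopsy, change in diet, assay variation) counts the same as a drug effect.

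The equivalence test does not close the gap. Two inert regimens that move together will pass it, so a marker can appear to have changed in both aspirin arms and to have changed equivalently with no drug effect at all.

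The trial has a randomised group that could separate the two explanations, with biopsies at the same visits. The plan does not say which arms the mixed models compare, whether placebo is one of them, at which time point, or which result governs if a paired test is significant and a placebo comparison is not. At stake are statements that aspirin changes the TUNEL and pMLKL ratios, COX-2, BAX, TRPM7, the joint indices, methylation or microbiota. The primary equivalence analysis is not at issue.

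**Working it through.** **Inputs from the documents**
- Allocation 40 : 40 : 10 (Section 13.1).
- 20% dropout, giving 32 per aspirin arm (Section 13.4). Placebo completers: 10 × 0.8 = 8. Total 32 + 32 + 8 = 72, the figure in Section 3.
- Pre-post correlation 0.5 (Section 13.4, primary endpoint). Then Var(change) = 2σ²(1 − 0.5) = σ², so the SD of change equals the baseline SD.

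**Assumptions, not in the documents**
- Size of a common drift: shown from 0 to 0.75 SD of change.
- Two-sided 0.05 for the paired tests, and normal changes.
- The 0.5 correlation is carried over to the other markers.

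**The plan's own figure.** The only powered analysis is the primary equivalence test: n = 32 per arm, margin 3.03, SD 4.04, true difference 0, alpha 0.05. SE = 4.04 × √(2/32) = 1.01. Exact power is 0.814, against 0.81 stated. The other two rows also reproduce (0.519 for 0.52, 0.911 for 0.91). No power is given for the paired tests or for any placebo contrast.

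**Paired test when aspirin is inert.** With a drift of d SD, the statistic follows a noncentral t on 31 df with noncentrality d√32 = 5.657d. It rejects beyond ±2.040. For either or both arms, the two arms are independent given the drift: 1 − (1 − p)² and p².

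| Drift (SD of change) | One aspirin arm significant | At least one | Both |
|---|---|---|---|
| 0 | 0.05 | 0.10 | 0.003 |
| 0.1 | 0.09 | 0.16 | 0.007 |
| 0.2 | 0.20 | 0.35 | 0.04 |
| 0.3 | 0.38 | 0.61 | 0.14 |
| 0.5 | 0.78 | 0.95 | 0.61 |
| 0.75 | 0.98 | 1.00 | 0.97 |

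**Adding the equivalence test.** In 40,000 simulated trials with inert aspirin and a fixed margin of 0.75 SD, equivalence was declared in 81% whether the drift was 0.5 SD or (to rounding, 82%) zero. At 0.5 SD drift, 56% of trials showed significant change in both arms together with equivalence.

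**Direct contrast with placebo.** In the same simulations, a two-sample t-test on change at 0.5 SD drift rejected in 4.8% of trials for one aspirin arm against placebo and 4.9% for both arms pooled.

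Its precision, with half-width = t × √(1/n₁ + 1/n₂):
- 32 v 8: 2.024 × √(1/32 + 1/8) = 2.024 × 0.395 = 0.80 SD. Power at a true effect of 0.5, 0.75 and 1.0 SD is 0.23, 0.46 and 0.69. 80% power needs 1.14 SD.
- 64 v 8: 1.994 × √(1/64 + 1/8) = 1.994 × 0.375 = 0.75 SD. Power is 0.26, 0.51 and 0.75. 80% power needs 1.07 SD.

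With no dropout at all, the half-widths would be 0.71 SD (40 v 10) and 0.67 SD (80 v 10).

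**The case against.** The strongest reply is that the plan already sees the problem. It includes placebo in the secondary analyses, plans mixed models that compare arms, and in Section 13.8 asks for 95% confidence intervals on all measurements of response. On that view only the naming of a contrast remains. Much of this stands: the data and the model are there, and the change is one of wording. What does not stand is that the between-arm comparison is settled. The models are listed as additional and exploratory, their arms are not identified, and nothing ranks them above the paired tests.

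Four stronger readings are tempting, and the documents do not support them:
- A reader might infer that the plan will treat drift as a drug effect. It does not say so. The paired tests are described only as examining whether markers change.
- A reader might take the remark that treatment-arm changes are hard to interpret as a general admission. In its full sentence it concerns methylation and microbiota only. The same limitation applies to the other markers as a matter of logic, but the plan does not state it for them.
- A reader might extend the point to every secondary endpoint. Fecal occult blood is compared between arms by Fisher's exact test.
- A reader might expect a significant aspirin arm to be set beside a non-significant placebo arm. That would mislead, since a paired test in 8 people detects a 0.5 SD drift with probability only 0.23. But the plan specifies no paired test in placebo, so an error rate for that comparison is not a property of this plan.

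It is also fair to say that the placebo contrast is weak. The one-SD effect that would give it power of 0.69 to 0.75 is an expectation for the primary ratio only, and nothing in the documents carries it to other markers. Weak precision is a reason to report a wide interval. It does not make a within-arm test an answer to the causal question.

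**Conclusion.** The point holds for the continuous secondary and exploratory markers. The two tests named for them cannot separate aspirin from common change over time, and the comparison that could is left without a defined contrast, time point or priority.

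The size depends on a drift that the documents do not give. With no drift, the paired test keeps its 5% error. At 0.2 SD of change, the chance that an inert arm looks active is about four times nominal (0.20), and at 0.5 SD it is 0.78. These figures rest on 32 completers per aspirin arm, normal changes and two-sided 0.05. The placebo contrast stays near 0.05 because a common drift cancels, but with about 8 placebo completers only effects of roughly 1.1 SD are detectable with 80% power.

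**What to change.** In Section 13.5:
- State that any conclusion about an effect of aspirin on a continuous marker rests on the difference in baseline-to-week-12 change between aspirin and placebo, with its 95% CI, from the planned mixed model with placebo included.
- Report it for each aspirin arm. Give the two arms pooled as a supporting estimate, noting that pooling presumes the regimens act alike, which the trial is itself testing.
- Apply this to all continuous markers, not only methylation and microbiota.
- Keep the paired and signed rank tests as descriptive summaries, and say that they are not evidence of a drug effect.
- State the precision in advance: half-width about 0.75 to 0.80 SD of change, power about 0.23 to 0.26 at 0.5 SD, and a non-significant contrast is not evidence of no effect.

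This costs SAP wording only, with no new participants, visits or assays. The intervals will be much wider than the within-arm ones: for a single arm of 32 the half-width is 2.040/√32 = 0.36 SD. Some markers that would have been reported as changed by aspirin will be reported as inconclusive.

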13. STATISTICAL CONSIDERATIONS

13.1 Study Design/Description

This is a Phase IIa, 3 arm, randomized placebo-controlled trial (40 subjects in each of two treatment arms and 10 subjects in the placebo arm) to evaluate whether, use of aspirin at 325 mg in a three weeks on/three weeks off regimen has similar/equivalent efficacy. Our hypothesis is that intermittent use group will show equivalent reduction in the primary endpoint (proliferation: apoptosis ratio) and reduced risk of adverse events, as that using aspirin daily.

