13.4 Primary Objective, Endpoint(s), Analysis Plan

The primary endpoint will be the ratio of proliferation to apoptosis biomarkers (Ki67 index: BAX index, measured continuously) in colorectal mucosa. We anticipate that the two treatment arms are “equivalent” with regard to this main outcome, in the manner described below, for which power analysis is provided. The statistical analysis will consist of examining whether two means are within prescribed limits from each other. Alternatively, two one sided tests can be performed. We have $n_1=n_2=32$, which is 40 less 20% dropout; $40-8=32$.

Power analysis for the main outcome

The main outcome is defined as the ratio $R = P/A$, where P for measure of Proliferation and A stands for measure of Apoptosis. In principle, intervention increases the Apoptosis and decreases Proliferation,

resulting in R decreasing.

We will measure R for each subject, in each treatment group at baseline (Clinic Visit 2) and at three months (Clinic Visit 4; 12 weeks), obtaining $R(i, j)$, where $i = 0, 3$ months is the time point, and $j = 1, 2$ represents the treatment arm. We will then obtain within-subject changes $D(j) = R(3, j) - R(0, j)$ for each subject. We expect R to decrease in both groups.

We will then compare mean changes in R between arms to show their equivalence, which we expect, is supported by statistical evidence. To this end, we compute power of a test of equivalence, as defined by following considerations.

The existing information on $R = P/A$ is scant. From [name] ongoing R01 randomization trial (R01 CA149633; PI: [name]) we have that $CV = SD/\text{mean of distribution of } R$ is in the range of 1.5-2 (150-200%).

Variable	Mean	Std Dev
A_P_overall	0.1825	2.5884
A_P_surface	3.2685	4.6094
A_P_bottom	0.0679	3.7236
P_A_overall	2.5444	4.0427
P_A_surface	0.306	4.6094
P_A_bottom	14.733	3.7236

This will limit our ability to argue in favor of equivalence using the usual cutoff points of 10% and 20%. Thus we will have to settle on a broader interval, namely that of 3/4 of standard deviation previously observed in the similar data.

We will assume the correlation between time = 0 and time = 3mo to be $\text{Corr}[R(3, j), R(0, j)] = 0.5$. Simple calculation shows that if pre and post variances are equal to each other σ^2 , then $\text{Var}[D(j)] = \sigma^2$, and thus theoretical standard deviation $SD[D(j)] = \sigma$.

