13.7 Evaluation of Toxicity

All participants will be evaluable for toxicity from the time of their first dose of aspirin.

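### Section 13.5 uses Fisher's exact test for fecal occult blood because events should be rare, which is where that test is most conservative; Boschloo's exact test would be a free improvement, not a correction of an error

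*Combined protocol and SAP*

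**What the plan says.** Section 13.1 gives the trial a two-part hypothesis: an equivalent reduction in the biomarker ratio on the intermittent schedule, and "reduced risk of adverse events, as that using aspirin daily". Section 2.3 names the expected advantage as less gastrointestinal bleeding.

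The measure of that advantage is secondary objective 3, "fecal occult blood test (measures of adverse events) as measured by stool samples". Section 13.5 makes each result binary at each visit. The proportion of participants with one or more positive results then "will be compared between arms using Fishers exact test because incidence of this adverse event is expected to be low".

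This is the only between-arm test of bleeding that the documents describe. Section 13.7 only defines who counts: "All participants will be evaluable for toxicity from the time of their first dose of aspirin". The allocation is "40 subjects in each of two treatment arms and 10 subjects in the placebo arm".

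For this comparison the documents give no incidence, alpha, sidedness or power, and they do not say which of the three arms are compared. The 5% level in section 13.4 belongs to the primary equivalence test.

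**The concern.** Fisher's test conditions on the total number of positive participants. With few positives only a handful of tables are possible, and the attainable p-values jump past 0.05 instead of landing near it. The true type I error then falls far below the nominal level, and power falls with it. The plan's reason for choosing the test is therefore also the condition under which it is least efficient.

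An unconditional exact test fixes only the two arm sizes and takes the worst case over the unknown common rate. Boschloo's version uses Fisher's p-value as its statistic and rejects up to the largest cutoff that still holds 5%.

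At stake is some power on the one formal comparison that addresses the hoped-for safety advantage.

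**Working it through.** **Plan's own figures.** None exist for this test. The only power figures in the documents are for the primary equivalence test at 32 per arm (0.52, 0.81, 0.91). They recompute as 0.519, 0.814 and 0.911, and they do not bear on this point.

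**Inputs.**
- 40 per aspirin arm (section 13.1). Section 13.7 counts all dosed participants, so this is the base case.
- 32 per arm as the sensitivity case. Section 13.4 describes its figure as one "which is 40 less 20% dropout": 40 − 8 = 32.
- Assumed: daily v intermittent, two-sided 5%.
- Assumed: common rates of 1% to 10% for size, and a range of unequal rates for power.

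**Formula.** With n per arm and rejection region R, the probability of rejecting is the sum over all tables (x, y) in R of b(x; n, p1) × b(y; n, p2), where b is the binomial probability. Setting p1 = p2 gives the true size.
- Fisher: R is every table with two-sided Fisher p ≤ 0.05.
- Boschloo: R is every table with Fisher p ≤ c, where c is the largest cutoff whose size, maximised over the common rate, is at most 5%. At 40 v 40, c = 0.0707.

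**Where Fisher starts to reject, 40 v 40.** For k v 0 positives the two-sided p is 2 × C(40,k)/C(80,k).
- 5 v 0: 2 × 658,008 / 24,040,016 = 0.0547, not rejected. Boschloo p = 0.033.
- 6 v 0: 0.0255, rejected by both.
- 7 v 1: Fisher 0.0568, Boschloo 0.033.

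At a 5% rate in both arms, 80 × 0.05 = 4 positives are expected in the whole comparison. Fisher's smallest rejecting table needs six, all in one arm.

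**True size, 40 v 40.**

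| Common rate | Fisher | Boschloo |
|---|---|---|
| 1% | <0.001% | <0.01% |
| 2% | 0.01% | 0.11% |
| 5% | 0.40% | 1.43% |
| 10% | 1.68% | 3.07% |
| Maximum over all rates | 3.30% | 4.77% |

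Fisher's own maximum is below 5%, so c cannot be smaller than 0.05. Boschloo's region therefore contains Fisher's, and its power can never be lower.

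**Power, 40 v 40.**

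| Daily v intermittent | Fisher | Boschloo | Gain (points) |
|---|---|---|---|
| 5% v 1% | 0.01 | 0.03 | 2.4 |
| 5% v 0% | 0.01 | 0.05 | 3.4 |
| 10% v 5% | 0.04 | 0.08 | 3.8 |
| 20% v 10% | 0.16 | 0.20 | 3.8 |
| 25% v 5% | 0.65 | 0.70 | 5.7 |
| 20% v 5% | 0.41 | 0.48 | 7.3 |
| 10% v 2.5% | 0.09 | 0.18 | 8.2 |
| 15% v 0% | 0.57 | 0.74 | 16.9 |
| 12.5% v 0% | 0.38 | 0.57 | 18.8 |

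**Sensitivity to dropout.** At 32 per arm Fisher's size is 0.19% at a 5% rate and 1.08% at 10%. The gain runs from 1.2 points (5% v 1%) to 19.0 points (15% v 0%).

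**Sensitivity to sidedness.** With a one-sided 5% test at 40 per arm and a 5% common rate, the size is 0.73% for Fisher and 2.25% for Boschloo. The gain over the scenarios run is about 6 to 21 points, so the point does not depend on the two-sided assumption.

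**The case against.** The strongest reply is that the plan contains no mistake. Fisher's test is standard and holds the type I error, and the documents attach no power claim or decision rule to this comparison. That stands in full: this is a matter of efficiency.

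Several stronger readings are tempting and should be resisted.

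- *A reader might infer that the test runs at 0.4% and that switching gains 6 to 17 points.* The 0.4% needs a 5% rate in both arms, 40 per arm and a two-sided test. Gains of that size need a daily-arm rate of about 10% or more. When both rates are 5% or less, the gain is 2 to 3 points and power stays below 5% with either test.
- *A reader might infer that 5 v 0 or 7 v 1 would be reported as non-significant.* That holds only for a two-sided test. The hypothesis is directional, and one-sided Fisher p-values are 0.027 and 0.028. The documents do not say which applies.
- *A reader might infer that half of the trial's hypothesis rests on this test.* The result is a secondary objective and, in section 8.2, a safety-monitoring measure. Adverse events are also recorded with grade and attribution (section 11.1), although no other between-arm test of them is specified.
- *A reader might infer that the change costs nothing in any sense.* It adds no participants and respects the 5% limit, but the power comes from spending more of that limit: 1.43% instead of 0.40% at a 5% rate.

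It can also be said that the change does not rescue the comparison. That is true: Boschloo's power is still 0.18 for 10% v 2.5%. It is the reason for asking for an interval as well. Section 13.8 requires 95% confidence intervals for measurements of response, and it is doubtful that this covers a safety proportion.

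**Conclusion.** A free improvement to a valid plan. Low incidence justifies an exact test but not the conditional one in particular. Under the stated assumptions, Fisher's test uses between almost none and about a third of its 5% at common rates of 1% to 10% (1.68 / 5 = 0.34). Boschloo's test holds the same limit and cannot do worse. The benefit ranges from about 2 to 19 points of power at 40 per arm and about 1 to 19 at 32. It is smallest where events are rarest.

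The size of the gain rests on incidences, alpha, sidedness and a pair of arms that the documents do not give. Two findings do not rest on the assumed incidences: Boschloo's maximum size at these arm sizes, and its region containing Fisher's. A non-significant result should not be read as evidence of equal bleeding risk under either test.

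**What to change.** Before unblinding, amend section 13.5 as follows.

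1. Name the comparison: daily v intermittent aspirin.
2. Replace Fisher's exact test with Boschloo's exact test, two-sided at 5%, and state how the two-sided p-value is formed. The statistic must be named, because other unconditional tests behave differently. The pooled-Z version has a size of 3.78% at a 5% common rate, against 1.43% for Boschloo.
3. Report the difference in proportions with an unconditional exact 95% confidence interval, and treat that interval as the main result for this endpoint.

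The cost is a few lines of text and standard software. No participants, visits or samples are added, and the 5% limit is kept.
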